7.0 STATISTICS

7.1 STATISTICAL HYPOTHESES AND SAMPLE SIZE JUSTIFICATION

This is a prospective, single-arm, multi-center, international clinical investigation to evaluate the safety and effectiveness of the PQ Bypass System, delivery guidewires, and implant stent grafts for percutaneous

femoropoliteal bypass compared to Performance Goals (PG). There are two hypotheses for the study. One is for the primary effectiveness endpoint – primary patency within 12 months, and one is for the primary safety endpoint – freedom from major adverse events (MAE) through 30 days.

7.1.1. Primary Effectiveness

The primary effectiveness endpoint is defined as primary patency at 12 months as evidenced by a peak systolic velocity ratio (PSVR) ≤ 2.5 from DUS and no clinically-driven re-intervention within the stented segment.

The primary effectiveness endpoint hypotheses are:

- H0: 12-month success rate of the PQ Bypass System $\leq 60.4\%$
- HA: 12-month success rate of the PQ Bypass System $> 60.4\%$

Based on a PG of 60.4%, a sample size of 202 with 181 subjects having evaluable data at 12 months would provide 91% power to test the primary effective hypothesis at the one-sided alpha level of 0.025, if the “true” PQ Bypass Stent Graft success rate is at least 72%. The Exact Test Method and commercial software PASS14 was used to determine the sample size.

In order to ensure sufficient subjects are available at 12 months for assessment of the primary effectiveness endpoint (i.e., to account for missing data), an additional 21 subjects (approximately 10% estimated attrition rate) may be enrolled, making the total study sample size equal to 202 TASC II D and complex TASC C subjects.

To meet the primary effectiveness endpoint of the IDE Study with a sample size of 202 enrolled and 181 evaluable subjects with 12 month primary patency data, at least 124 subjects ($\geq 68.1\%$) must experience 12-month primary patency (calculated using the exact confidence interval).

7.1.2. Primary Safety

The primary safety endpoint of the PQ Bypass Detour II IDE Study is the freedom from MAE rate at 30 days following stent graft implantation, and includes:

- Death
- Target lesion revascularization (TLR)
- Amputation of the index limb
- Symptomatic deep vein thrombosis (DVT)
- Pulmonary embolism (PE)
- Procedure related bleeding requiring any transfusion of packed red blood cells or surgery

The primary safety endpoint hypotheses are:

- H0: 30-day Freedom from MAE rate of the PQ Bypass System $\leq 84\%$
- HA: 30-day Freedom from MAE rate of the PQ Bypass System $> 84\%$

The rate of freedom from 30-day MAE for the PQ Bypass System is expected to be no less than 92%. Based on a PG of 84% and an estimated 30-day freedom from MAE rate of 92% for the PQ Bypass System, a sample size of 169 evaluable subjects provides 88% power to test the primary safety hypothesis at the one-sided alpha level of 0.025. The Exact Test Method and Commercial software PASS14 was used to determine the sample size. The final sample size is based on the number required to test the primary effectiveness hypothesis (N=181 including attrition). The primary analysis population will include 202 TASC II D and complex TASC C subjects.

To meet the primary safety endpoint of the IDE Study with a sample size of 181 evaluable subjects (the actual number of subjects who are free from MAEs at 30 days MAE can be no less than 163 subjects ($\geq 89.6\%$)).

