7.3.1. Missing Data

Subjects free from clinically-driven target lesion revascularization within the stented segment but do not have sufficient follow-up to assess the primary effectiveness endpoint will be treated as having missing data for the primary effectiveness endpoint. To further evaluate the impact of missing data on the primary

effectiveness endpoint, Kaplan-Meier methods, will also be used to estimate the 12-month primary patency rate.

For the primary safety endpoint analysis, the denominator for each parameter in the safety measures will be the number of subjects who had sufficient follow up (at least 23 days for 30-day visit) plus any subjects who had an event prior to the milestone visit.

All subjects will be accounted for in the study report, including the reasons for any subjects exiting the study early.

Every effort will be made to collect all data points contributing to the primary effectiveness endpoint in the study. The sponsor attempts to minimize the amount of missing data by appropriate management of the prospective clinical trial, proper screening of study subjects, and training of participating investigators, monitors and study coordinators. In order to further assess the potential impact of missing data on the primary effectiveness endpoint analyses, the following sensitivity analyses will be performed:

- Worst-Case Scenario: Each missing value for the primary effectiveness endpoint will be treated as a failure. If this still results in rejection of the null hypothesis then no further missing data imputation analyses will be performed for the endpoint.
- If the conclusion is not upheld with the worst-case scenario approach, then the multiple imputation method will be used. A logistic regression model will be used and fifteen imputed datasets will be generated.
- Additionally a tipping point analysis will be performed. The proportion of missing values assigned the status of 'failure' will be sequentially increased to identify the point at which the study conclusions change (i.e., the null hypothesis is no longer rejected).

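### Section 7.1.2 labels 181 as the sample size including attrition when Section 7.1.1 makes that 202, and its only safety power (88% at 169) is 86.9% under the stated exact method, with none given for 181 or 202

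*Combined protocol and SAP*

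**What the plan says.** Section 7.1.2 (Primary Safety) tests freedom from 30-day MAE against a goal of 84%, with an expected rate of 92%. It states that "a sample size of 169 evaluable subjects provides 88% power to test the primary safety hypothesis" at a one-sided alpha of 0.025, and gives the method: "The Exact Test Method and Commercial software PASS14 was used to determine the sample size". It continues: "The final sample size is based on the number required to test the primary effectiveness hypothesis (N=181 including attrition"). It then names 202 subjects as the primary analysis population, and ends with a pass mark for 181 evaluable subjects.

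Section 7.1.1 (Primary Effectiveness) uses the same two numbers differently: "a sample size of 202 with 181 subjects having evaluable data at 12 months would provide 91% power". It adds 21 subjects for roughly 10% attrition, which brings the total to 202.

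The safety denominator is set elsewhere. Section 7.3.1 counts "the number of subjects who had sufficient follow up (at least 23 days for 30-day visit"), plus anyone with an earlier event. Section 7.5.1 applies this to the ITT set and requires the lower exact one-sided 97.5% limit to exceed 84%.

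**The concern.** The two halves of the sample-size section contradict each other on which number includes attrition. This is the justification for one of the trial's two primary hypotheses, so the label and the power should be right.

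The stated power also belongs to a size, 169, that is neither the size of the printed pass mark (181) nor the enrolled total (202). The 10% allowance behind 181 is for missing 12-month patency data, whereas safety is read at 30 days on the ITT set. The safety denominator could therefore be larger than 181, and the plan gives neither an expected value nor a power for it. What is at stake is the accuracy of the stated design properties, not the validity of the test.

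**Working it through.** **Inputs.** Goal p0 = 0.84, assumed true rate p1 = 0.92, one-sided alpha 0.025, exact method and n = 169 (all Section 7.1.2). Evaluable 181, added 21, total 202, attrition about 10% (Section 7.1.1). Decision rule: exact lower 97.5% limit above 84% (Section 7.5.1).

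**Attrition label.** Total = evaluable / (1 − attrition) = 181 / 0.90 = 201.1, rounded up to 202. Also 181 + 21 = 202, and 21/202 = 10.4%. So 181 is the number left after attrition and 202 is the number including it.

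**The plan's own power figure.** Let X be the number of subjects free from MAE. The pass mark r is the smallest count with P(X ≥ r | n, p0) ≤ 0.025. This is equivalent to the Section 7.5.1 confidence-limit rule. Power is P(X ≥ r | n, p1).

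At n = 169:
- r = 151 gives a tail of 0.0318 under 0.84, which is too large.
- r = 152 gives 0.0183, so the pass mark is 152 (89.9%).
- Power = P(X ≥ 152 | 169, 0.92) = 0.869, against the stated 88%.

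A one-sample normal approximation gives Φ[(0.08·√169 − 1.96·√(0.84·0.16)) / √(0.92·0.08)] = Φ[(1.040 − 0.719) / 0.271] = 0.882. That is close to the printed 88%, but it is not the method the section names.

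**Exact power at the operating sizes.**

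| n | pass mark | attained alpha | power at 92% |
|---|---|---|---|
| 169 | 152 | 0.0183 | 86.9% |
| 181 | 162 | 0.0232 | 91.1% |
| 187 | 168 | 0.0150 | 88.7% |
| 195 | 174 | 0.0248 | 93.5% |
| 202 | 181 | 0.0152 | 91.3% |

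Exact power moves in a sawtooth because the pass mark is a whole number. Over every n from 181 to 202 the lowest value is 88.7% (n = 187) and the highest 93.5% (n = 195).

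The 91.1% at 181 uses the pass mark of 162 that follows from Section 7.5.1. Section 7.1.2 prints 163 (given as 89.6%, although 163/181 = 90.1%). With 163 at n = 181, alpha would be 0.0132 and power 86.4%. That mismatch is a separate matter, but it should be settled when the power is restated.

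**The case against.** The strongest reply is that this is a slip in one parenthesis. With two primary endpoints it is normal to size each and enrol to the larger. Section 7.1.2 does this openly: 169 is enough for safety, and effectiveness sets the final size. Its last sentence calls 181 evaluable, in agreement with Section 7.1.1. The gap between 88% and 86.9% is about one point and changes no decision. Power is at least 88.7% anywhere from 181 to 202, so the printed 88% works as a slightly conservative floor.

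Most of this stands, and it rules out several stronger readings that a reader might draw:

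- *That the safety test is planned on 169, so the stated figures describe no test the trial will run.* The documents do not support this; 169 is a safety-only minimum.
- *That one cannot tell how the safety decision will be made.* Section 7.1.2 names 181 evaluable for the pass mark, and Sections 7.3.1 and 7.5.1 define the test for any denominator.
- *That the safety denominator will be close to 202.* The documents give no 30-day evaluable number. Section 4.8 lets subjects with aborted procedures exit after discharge. Those who leave event-free before day 23 would drop out of the denominator, and their number is not stated.
- *That safety is underpowered.* The calculation shows the opposite.

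What the reply does not remove is that the label is wrong, that the power is not what the named method gives, and that no power is stated at the sizes to which the safety test is tied.

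**Conclusion.** The point holds as an error of statement in the justification of a primary endpoint. The attrition label is wrong by the plan's own arithmetic: the size including attrition is 202, not 181. The stated safety power is about one point too high under the stated method (86.9% against 88%), and safety power at the operating sizes is missing.

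The consequence is small and does not favour the sponsor: power at 181 to 202 (88.7% to 93.5%) is above the printed 88% throughout. These figures assume a true rate of 92%, a goal of 84%, one-sided alpha 0.025 and the exact rule of Section 7.5.1. Where in the range up to 202 the 30-day denominator will fall cannot be settled from the documents. Enrolment, hypotheses, analysis set and decision rule are unaffected.

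**What to change.** In Section 7.1.2:

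1. Change the parenthesis to: *N=202 including attrition; 181 evaluable at 12 months*.
2. Keep 169, described as the minimum size for the safety hypothesis alone, and restate its exact power as about 87%.
3. Add exact safety power at the operating sizes: 91.1% at 181, 91.3% at 202, and 88.7% to 93.5% across 181 to 202.
4. If an expected 30-day evaluable ITT number is given, state it as an assumption that allows for aborted cases exiting after discharge (Section 4.8).
5. Bring the printed pass mark for 181 into line with the Section 7.5.1 rule.

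The cost is a wording change to the protocol and SAP text, with no effect on enrolment, data collection or the analysis rule.

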7.2 ANALYSIS POPULATIONS

Analysis populations include the Intention to Treat (ITT), Modified Intention to Treat (MITT) and Per Protocol Cohorts. The primary analysis will be on the TASC II D and complex C population excluding roll-ins.

7.2.1. Roll-in Cohort

The first two subjects at each U.S. site may be considered a roll-in subject. Roll-in subject will be pre-identified. Baseline characteristics and safety and efficacy outcomes for this cohort

will be reported separately and be purely descriptive. The roll-in cohort will be excluded from hypothesis testing and from the ITT and MITT populations.

7.2.2. Intention to Treat (ITT)

The ITT Cohort includes all subjects enrolled in the IDE Study. The ITT Cohort will be the primary analysis population to determine if the primary safety endpoint was met in the study.

7.2.3. Modified Intention to Treat (MITT)

The MITT Cohort includes only those subjects/lesions where a PQ Bypass System Stent Graft was implanted. The MITT cohort is a subset of the ITT Cohort. The MITT Cohort will be the primary analysis population to determine if the primary effectiveness endpoint was met in the study.

7.2.4. Per Protocol

The per protocol population is a subset of the MITT group which will exclude all subjects with major protocol deviations (e.g., violations of eligibility criteria, or DAPT compliance).

7.3 GENERAL STATISTICAL CONSIDERATIONS

Demographic, baseline clinical and disease characteristics and procedural results will be summarized in tables for both ITT and MITT populations. For continuous variables, the summary will include the number, mean, median, standard deviation, minimum and maximum. Summaries for categorical variables will include the number and percent of subjects in each category. Confidence intervals may be presented, where appropriate, using the t-distribution for continuous data and the Exact binomial method for categorical variables. Statistical analyses will be performed using SAS for Windows version 9.4 or higher.

DATA CONSIDERATIONS

7.3.1. Missing Data

Subjects free from clinically-driven target lesion revascularization within the stented segment but do not have sufficient follow-up to assess the primary effectiveness endpoint will be treated as having missing data for the primary effectiveness endpoint. To further evaluate the impact of missing data on the primary

effectiveness endpoint, Kaplan-Meier methods, will also be used to estimate the 12-month primary patency rate.

For the primary safety endpoint analysis, the denominator for each parameter in the safety measures will be the number of subjects who had sufficient follow up (at least 23 days for 30-day visit) plus any subjects who had an event prior to the milestone visit.

All subjects will be accounted for in the study report, including the reasons for any subjects exiting the study early.

Every effort will be made to collect all data points contributing to the primary effectiveness endpoint in the study. The sponsor attempts to minimize the amount of missing data by appropriate management of the prospective clinical trial, proper screening of study subjects, and training of participating investigators, monitors and study coordinators. In order to further assess the potential impact of missing data on the primary effectiveness endpoint analyses, the following sensitivity analyses will be performed:

- Worst-Case Scenario: Each missing value for the primary effectiveness endpoint will be treated as a failure. If this still results in rejection of the null hypothesis then no further missing data imputation analyses will be performed for the endpoint.
- If the conclusion is not upheld with the worst-case scenario approach, then the multiple imputation method will be used. A logistic regression model will be used and fifteen imputed datasets will be generated.
- Additionally a tipping point analysis will be performed. The proportion of missing values assigned the status of 'failure' will be sequentially increased to identify the point at which the study conclusions change (i.e., the null hypothesis is no longer rejected).

7.3.2. Data Pooling

Poolability analyses will be performed on primary safety and effectiveness endpoint results to determine if subjects enrolled in different regions (U.S. vs. Outside the US, (OUS)) and subjects at different sites can be pooled.

7.3.2.1. Poolability by Region

To determine if region (U.S. vs. OUS) has an effect on primary safety and effectiveness outcomes, a poolability by region analysis will be performed which compares the primary effectiveness and primary safety endpoint results between subjects enrolled in the U.S. vs OUS.

Comparisons will be made using Fisher's Exact Test and poolability will be assessed at the 0.15 significance level. If the p-value is non-significant ($p \geq 0.15$) then the regions will be considered poolable. If the differences are significant ($p < 0.15$), then baseline characteristics will be compared between the U.S. and OUS regions. Since this is a single arm study, differences in outcomes could be due to differences in baseline characteristics by region or due to difference in device performance. To better understand the underlying cause of apparent differences, a model will be fit that includes region, as well as any baseline characteristics that differ significantly by region.

7.3.2.2. Site by Site Poolability

To determine if individual sites have an impact on primary safety and effectiveness endpoint results, a site-by-site poolability analysis will be performed. Comparison will be made using Fisher's Exact Test and poolability will be assessed at the 0.15 significance level. If the p-value is non-significant ($p > 0.15$) then site results will be considered poolable. If the p-value is significant ($p \leq 0.15$) then the effect on the site by site comparison in the presence of any baseline characteristics found to be out of balance across sites will be analyzed. Sites having fewer than 5 subjects will be combined into low enrolling pseudo site pool group(s).

7.4 EFFICACY ANALYSES

7.4.1. Primary Effectiveness Analysis

The MITT cohort will be used to evaluate the primary effectiveness endpoint. All subjects in the MITT population that have a clinically-driven re-intervention within the stented segment that occurs within 360 days of the index procedure will be considered a failure for the primary effectiveness endpoint. All subjects free from clinically-driven re-intervention within the

stented segment who meet the definition of stent graft patency with at least 11 months (330 days) of follow-up will be considered successful with respect to the primary effectiveness endpoint. Subjects free from clinically-driven re-intervention within the stented segment but do not have sufficient follow-up to assess the primary effectiveness endpoint will be treated as missing data.

The primary effectiveness hypothesis will be tested by calculating the one-sided 97.5% confidence limit, using the Exact method. If the lower limit exceeds the performance goal of 60.4% the primary effectiveness hypothesis will be met.

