3.0 SELECTION AND WITHDRAWAL OF SUBJECTS

3.1 INCLUSION CRITERIA

All subjects are required to meet the following inclusion criteria in order to be considered eligible for participation in this trial:

General Inclusion Criteria

1. Age > 18 and ≤ 90 years of age.
2. Willing and able to provide informed consent.
3. Subject is willing to undergo all follow-up assessments according to the specified schedule over 36 months.

Clinical Inclusion Criteria

4. Chronic, symptomatic lower limb ischemia defined as Rutherford clinical categories 3, 4, or 5.
5. Venous Clinical Severity Score < 3.
6. Subject is a suitable candidate for angiography and endovascular intervention and, if required, is eligible for standard surgical repair.

Angiographic Inclusion Criteria

7. Symptomatic femoropopliteal chronic total occlusions ≥ 20 cm (TASC D) that can include de novo, restenotic, or in-stent restenotic lesions; *or*
Symptomatic femoropopliteal lesions ≥ 24 cm (total lesion length) that can include a chronic total occlusion or a ≥70% lesion that includes de novo, restenotic or in-stent restenosis (complex TASC C), by investigator visual assessment.
8. Reference vessel diameter ≥ 4.5 and ≤ 6.7 mm, by investigator visual assessment.
9. Subject has a patent popliteal artery (<50% stenosis) distal to the landing zone

10. Able to successfully access the SFA origin for entry of the crossing device.
11. At least one patent infrapopliteal vessel (<50% stenosis) with run-off to the ankle or foot.
12. A significant stenosis ($\geq 50\%$) or occlusion of an ipsilateral, inflow artery (e.g. aortoiliac, common femoral) must be successfully treated (use of investigational treatment prohibited) prior to treatment of the target lesion. Successful treatment is defined as no complications and less than 30% residual stenosis following intervention.

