4.2.3 Secondary Endpoints

1. Major Adverse Events (MAE) at 6, 12, 24 and 36 months
2. Major Adverse Limb Event (MALE) defined as above-ankle amputation or major reintervention including placement of a new bypass graft, interposition graft, thrombectomy, or thrombolysis
3. Major bleeding is defined as any bleeding event requiring transfusion of ≥ 2 units packed red blood cells (PRBC) or surgical repair through 30 days
4. Symptomatic Deep Vein Thrombosis (DVT) on ipsilateral limb at 30 days and 6, 12, 24 and 36 months
5. Pulmonary embolism at 30 days and 6, 12, 24 and 36 months
6. Perioperative myocardial infarctions through 30 days
7. Hematoma ≥ 8 cm related to the device or procedure through 30 days
8. The combined rate of death, target lesion revascularization (TLR), index limb amputation, and an increase in Rutherford Clinical ~~Becker~~ Classification by 2 classes (comparing pre- to post-procedural assessments) at 30 days and 6, 12, 24 and 36 months
9. Stent graft separation and migration identified via ultrasound imaging at 30 days and 6, 12, 24 and 36 months
10. Stent graft separation and migration identified via X-ray at 12 months
11. Stent graft fracture identified via X-ray at 12 months

12. Technical Success defined as successful delivery of the investigational devices to the identified area and removal of delivery system
13. Procedural Success defined as successful delivery of the investigational devices to the identified area and removal of delivery system in the absence of in-hospital MAEs
14. Clinical Success defined as limb ischemia improvement as assessed by Rutherford Clinical Classification (improvement in scale by ≥ 1) at 30 days and 6, 12, 24 and 36 months
15. Limb ischemia by Rutherford Clinical - Classification through follow-up at 30 days and 6, 12, 24 and 36 months
16. Primary Patency at 30 days and 6, 24 and 36 months
17. Primary assisted patency defined as revascularization of non-occlusive (<99%) stenosis within the stent graft or immediately above or below the treated arterial segment with less than 50% residual stenosis at 30 days and 6, 12, 24 and 36 months
18. Secondary patency defined as: revascularization of occlusion (100%) within the stent graft or immediately above or below the treated arterial segment with less than 50% residual stenosis at 30 days and 6, 12, 24 and 36 months

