19. Target Vessel Revascularization defined as any repeat percutaneous intervention or surgical bypass of any segment of the target vessel at 30 days, 6, 12, 24 and 36 months
20. Ankle-Brachial Index (ABI) or Toe Brachial Index (TBI) of both the index limb and contralateral limb at 30 days and 6, 12, 24 and 36 months
21. Number of major index limb amputations at 30 days and 6, 12, 24 and 36 months
22. Major procedure-related infections within 30 days
23. Length of post-procedure hospital stay
24. Length of ICU stay
25. Hospital re-admissions through 30 days
26. Change from baseline in VascuQol QOL Score at 30 days and 12 months

27. Change from baseline in EQ-5D-5L QOL Score at 30 days and 12 months
28. Change from baseline in Duplex Venous Observation Scale at 30 days and 6, 12, 24 and 36 months
29. Change from baseline in Villalta and Venous Clinical Severity (VCSS) Scales at 30 days and 6, 12, 24 and 36 months
30. SF-12 Score at Baseline, 30 days and 12 months

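### The failure and missing-data rules in 7.4.1 and 7.3.1 are narrower than the patency definition in 4.2.1, so some subjects with surgical bypass around the graft or amputation can be dropped as missing

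*Combined protocol and SAP*

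**What the plan says.** **Failure and missing rules.** In 7.4.1 the only event labelled a failure is the one in MITT subjects that "have a clinically-driven re-intervention within the stented segment that occurs within 360 days of the index procedure will be considered a failure". A success must be free of that event, meet the definition of stent graft patency and have at least 330 days of follow-up. Subjects free of the event whose follow-up is too short to assess the endpoint are missing. Section 7.3.1 repeats the restriction: "Subjects free from clinically-driven target lesion revascularization within the stented segment but do not have sufficient follow-up" are treated as missing. Sections 5.1 and 7.1.1 also confine re-intervention to the stented segment.

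**Endpoint definition.** Section 4.2.1 requires absence of CD-TLR and absence of stenosis above 50% on imaging, including 1 cm above and below the treated segment. The Section 15 entry for primary patency agrees: a velocity ratio above 2.5, angiographic stenosis above 50%, or CD-TLR each ends patency. The Section 15 entry for CD-TLR has no stented-segment limit and names neither percutaneous nor surgical procedures.

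**Where bypass and amputation appear.** Target vessel revascularization (4.2.3, item 19) is "any repeat percutaneous intervention or surgical bypass of any segment of the target vessel". The major adverse limb event (item 2) is "above-ankle amputation or major reintervention including placement of a new bypass graft" or certain other procedures. Amputation is also in the 30-day safety composite (4.2.2). Inclusion criterion 6 asks that the subject, "if required, is eligible for standard surgical repair". No effectiveness definition or analysis rule mentions either event.

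**Test.** "If the lower limit exceeds the performance goal of 60.4% the primary effectiveness hypothesis will be met", with an exact limit "at the one-sided alpha level of 0.025".

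**The concern.** The plan allows for surgery and amputation, but the primary analysis does not say how to score them. A bypass routed around the study graft is not, on plain reading, a re-intervention within the stented segment, and an amputation is not a re-intervention at all. After either event a 12-month duplex of the graft may not be done or may not be informative. If nothing else documents loss of patency, the missing-data rule is the one that applies.

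Such missingness is informative: the subject is unassessed because the treatment is likely to have failed. Removing a failure from the denominator turns x/(n+k) into x/n, which is always larger, so the error favours the device. The same bypassed subject could also be a failure under 4.2.1 and missing under 7.4.1. In a single-arm, open trial that choice should not remain open until the data are known.

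**Working it through.** **Inputs from the documents.** Performance goal 60.4%; one-sided alpha 0.025; assumed true success 72%; 181 evaluable of 202 enrolled; pass mark 124 (7.1.1). Exact lower limit: 7.4.1.

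**Input not given.** The number k of subjects with bypass or amputation who would be classed as missing. The CE Mark study (Table 4) had 0/80 limbs with major amputation at 12 months, for which the exact two-sided 95% upper limit is 1 − 0.025^(1/80) = 4.5%. It had 19/80 limbs with target vessel revascularization, with no surgical share stated. So k is an assumption, shown as a range.

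**1. The plan's own figures.** The smallest x with P(X ≥ x | 181, 0.604) ≤ 0.025 is x = 123 (tail 0.0216). Power is P(X ≥ 123 | 181, 0.72) = 90.1%, close to the plan's claim that the sample "would provide 91% power to test the primary effective hypothesis". The stated mark of 124 also passes, one above the exact minimum. Two side points: 124/181 is 68.5%, whereas the printed 68.1% fits 124/182; and 5.1 prints 191 evaluable where 7.1.1 prints 181.

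**2. Add k omitted subjects back as failures.** The lower limit is the 2.5% quantile of Beta(x, n − x + 1), with n = 181 + k.

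| Result as reported | k | Counted | Lower limit | Above 60.4%? |
|---|---|---|---|---|
| 123/181 | 0 | 123/181 | 60.63% | yes |
| 123/181 | 1 | 123/182 | 60.26% | no |
| 124/181 | 0 | 124/181 | 61.20% | yes |
| 124/181 | 1 | 124/182 | 60.83% | yes |
| 124/181 | 2 | 124/183 | 60.47% | yes |
| 124/181 | 3 | 124/184 | 60.11% | no |
| 124/181 | 5 | 124/186 | 59.40% | no |
| 126/181 | 5 | 126/186 | 60.51% | yes |
| 130/181 | 5 | 130/186 | 62.75% | yes |

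The last row is close to the planned result (0.72 × 181 = 130.3).

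**3. Effect on the type I error (illustration).** Take 181 subjects, a true success rate of exactly 60.4% when everyone is counted, and a share f who are all true failures and are all removed as missing. Success among those left is 0.604/(1 − f). With K ~ Bin(181, f) removed and c(n) the smallest passing count for n subjects, the error is Σ P(K = k) × P(Bin(181 − k, 0.604/(1 − f)) ≥ c(181 − k)).

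| f | Type I error |
|---|---|
| 0 | 2.2% |
| 1% | 3.2% |
| 2% | 4.4% |
| 3% | 6.1% |
| 5% | 11.8% |

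This is an upper picture for each f, because it assumes that no such subject is caught by imaging or by adjudication.

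**The case against.** A reader might infer that re-intervention within the stented segment is the only route to failure, so that bypassed or amputated subjects are never failures. The documents do not support that.

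- Success under 7.4.1 also requires patency, and imaging alone can end patency. A graft imaged as occluded has been assessed and is not missing.
- Table 1, footnote 3, requires angiography to go to the core laboratory for all target limb revascularization procedures. Qualifying imaging is thus expected around a bypass.
- CD-TLR is not limited to percutaneous procedures. A bypass for stenosis above 50% with recurrent ischemia fits its wording. The events committee adjudicates CD-TLR under charter definitions that are not in these documents.
- Section 7.3.1 has a worst-case analysis and a tipping-point analysis, both of which move missing subjects toward failure.

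It can also be said that amputation is not loss of patency, is already counted in safety and secondary endpoints, and can occur with an open graft. The performance goal comes from literature and approved-device data (Section 2.0), and the documents do not show whether those sources counted such events.

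All of this stands, and it narrows the point. It does not close it. The wider reading of CD-TLR conflicts with the operative sentence in 7.4.1. Amputation has no rule at all. The worst-case and tipping-point analyses are sensitivity analyses, and if the worst case overturns the result the plan goes to multiple imputation, which can assign success to some of these subjects. Section 7.3.1 states no event or censoring rule for the Kaplan-Meier estimate, so it cannot be said to censor them, nor to count them.

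**Conclusion.** The point holds as a gap between sections. The rules in 7.4.1 and 7.3.1 are narrower than the endpoint in 4.2.1 and Section 15. A subject with bypass around a failed graft, or with target-limb amputation, can be classed as missing if there is no qualifying imaging, no adjudicated CD-TLR and insufficient follow-up. The direction is certain: leaving such failures out can only raise the rate.

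The size is not known, because the documents give no rate. Three omitted failures reverse a result of 124/181, two do not, and one reverses 123/181. With up to five, a result of 126/181 or better still passes, so the trial's conclusion is at risk only close to the pass mark. Even so, rule-driven omission of true failures in 2% of subjects would about double the nominal error (2.2% to 4.4%), under the assumption that none is caught by other routes. That justifies settling the rule in advance.

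**What to change.** 1. In 7.4.1 and 7.3.1, and in the matching wording of 5.1 and 7.1.1, replace re-intervention within the stented segment with CD-TLR as used in 4.2.1, or loss of patency on imaging.
2. In the Section 15 definition, state that CD-TLR includes surgical bypass performed for failure of the treated segment.
3. Count above-ankle amputation of the target limb as a failure on its date, unless the events committee documents a patent graft. Do not treat it as missing.
4. Use the same events and dates in the Kaplan-Meier estimate.

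**Cost.** Mostly wording; bypass and amputation are already collected as secondary endpoints. Section 12 names major amputation and CD-TLR for adjudication but not bypass, so the committee's remit must be extended to bypass procedures. The patency rate may come out slightly lower. The sponsor should also check that the wider event set matches the way the 60.4% goal was derived.
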